#### Others:

- Improvement in the subject’s coexisting disorders as measured by the corresponding scales below, as compared with baseline measures to the blinded period:
  - Migraine: Migraine Disability Assessment Test (MIDAS)
  - Anxiety and Depression: Hospital Anxiety and Depression Scale (HADS)
- Comparison of active versus sham device data as to change in the use of pain or headache medications taken at the end of the randomized/blinded period compared to baseline.
- Adverse events

	Protocol Name:	Vagus Nerve Stimulation: A Non-Invasive Treatment to Improve the health of Gulf Veterans with Gulf War Illness
	Principal Investigator:	[name]
	Primary Contact Name/Contact Info:	[name]: [contact]
	Date Revised:	07/15/2019
	Study Number:	HSM# 16-00097

- A subject's study participation would stop if a patient's symptoms became such that the patient requested stopping or the study doctor felt symptom severity required stopping.

## f) Procedures Involved in the Human Research

### Source data to be used in Study

*Numerical Rating Scale:* This is a zero to 10 visual analog scale asking veterans to rate the severity of their body-wide pain in the last 24 hrs where zero is no pain and 10 is worst pain possible.

*Kansas Criteria:* These criteria are followed in diagnosing Gulf War Illness. This is done via the history which collects medical information used to diagnose GWI through the endorsement of musculoskeletal pain at moderate or severe intensities. In addition to pain, veterans must endorse symptoms in at least 2 more of the following problem areas: Fatigue/sleep; cognitive and mood; Gastrointestinal; respiratory; skin.

*SF-36:* This is a 36 question vehicle used to assess a patient's health related quality of life. The version for veterans will be used. The physical function subscore will be one of the outcome measures

*Patient Global Assessment of Change:* This scale consists of 7 questions, each scored with a scale ranging from +3 [very much improved] through 0 [no change] to -3 [very much worse]

*Number of migraine days in the past week:* A migraine day is one where a patient has a headache lasting at least 4 hours

*Diary:* Patients will be required to complete a diary after they self administer each treatment to each side of his/her neck. The diary asks the time of the treatment and the stimulus intensity elected by the subject. After the final treatment for that day, the diary asks the patient if s/he has had a headache lasting at least 4 hours.

*Electronic Diary:* Patients will be required to complete a diary after they self administer each treatment to each side of his/her neck. The electronic diary asks the time of the treatment and the stimulus intensity elected by the subject. After the final treatment for the day, the diary asks the patient if s/he has had a headache lasting at least 4 hours. The electronic diary mirrors the paper diary, except that it is online with a secured web address. The subject can access with any electronic device with the capability of accessing the internet. A subject is given a unique 10 digit subject number to access the website. No other information is collected by the subject. Upon logging in for the first time, the subject creates a password and is the only person that can log into their eDiary. This is given as an option for subjects who prefer to use the electronic version over the paper version.

*Migraine Disability Assessment Test (MIDAS):* This is a 7 item questionnaire that assesses the effect that migraine has on a patient in the past 2.5 months.

*Hospital Anxiety and Depression Scale (HADS):* This is a 14 item questionnaire that quantifies the amount of anxiety and/or depressed mood a subject has had in the past week.

*Measure of Certainty Questionnaire:* This is a four choice vehicle that asks a subject how certain s/he was that s/he was getting the active treatment.

	Protocol Name:	Vagus Nerve Stimulation: A Non-Invasive Treatment to Improve the health of Gulf Veterans with Gulf War Illness
	Principal Investigator:	[name]
	Primary Contact Name/Contact Info:	[name]: [contact]
	Date Revised:	07/15/2019
	Study Number:	HSM# 16-00097

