#### Secondary:

- Change in the Patient’s Global Impression of Change (PGIC) scale scores of overall symptom burden as completed by the subject from study onset to end of the blinded phase of the trial. Assessment of this endpoint will be based on a comparison between change occurring in active-treated versus sham-treated.
- Change in physical function subscale of the SF-36, a questionnaire assessing health related quality of life from study onset to end of the blinded phase of the trial. Assessment of this endpoint will be based on a comparison between change occurring in active-treated versus sham-treated.
- The difference between the active and sham treatment groups in change in number of migraine/headache days in the final week of the randomized/blinded period from the week prior to randomization.

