**Blinded Phase of Study**

Encounter 6 – Office Visit [first time at ISMMS]: Confirmation of eligibility, randomization and device and diary training Visit. Subjects deemed eligible for study participation up to this point, will be invited to ISMMS in the Annenberg Building located at [name], within one week after Visit 5. They will sign consent for study participation. They will provide a fifth rating of widespread pain severity over the past 24 hours at this encounter on a 10-point VAS. The fifth pain rating will be added to the 4 VAS pain ratings done in the week after intake at the VA. If the median of all 5 VAS widespread pain ratings remains at least a 5, subjects remain eligible to participate. Then medical and eligibility information obtained on Encounters #1 through 5 will be briefly reviewed, a pregnancy test will be administered, and a medication history will be taken. If still deemed eligible to continue on in the study, they then complete questionnaires [MIDAS, SF-36 and HADS] and undergo a brief baseline medical evaluation consisting a physical examination including vital signs and a tender point examination and of asking the veteran questions to determine if s/he fulfill criteria for chronic fatigue syndrome, fibromyalgia, and/or irritable bowel syndrome and for Gulf War Illness. Subjects are then randomized and trained by the blinded trainer to use the device to which they have been assigned [devices are received with serial numbers covered and numbered sequentially so the trainer is blinded to condition]. Subjects will receive identical instruction and guidelines regardless of which device they receive. To be sure the subject knows how to use the device; s/he will be given a quiz about using the device after training. They will also be trained on use of a daily diary (paper and electronic) to be completed after each of the three daily treatments. Subjects will be given an unique 10 digit identifier that they will used to log into the Merge IBM site, in which they will be prompted to create a username and password.

Veterans will be reminded [as specified in the study consent form] that in order to proceed to the open label phase of the study, they must administer at least 70% of all programmed stimuli as well as complete at least 70% of the diary entries; however, because the device needs to be sent back to the

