	Protocol Name:	Vagus Nerve Stimulation: A Non-Invasive Treatment to Improve the health of Gulf Veterans with Gulf War Illness
	Principal Investigator:	[name]
	Primary Contact Name/Contact Info:	[name]: [contact]
	Date Revised:	07/15/2019
	Study Number:	HSM# 16-00097

manufacturer in order to obtain the stimulation data, resulting in a 3-4 day delay in retrieving the data, we will not be able to use this criterion to advance subjects to get an actual unit in the open label phase of the study. Therefore, although we will tell subjects they have to deliver at least 70% of all programmed stimuli in order to get an active unit, the only criterion that will be enforced is that they will have had to complete 70% of diary entries, which will be verified by reviewing their diary logs at Encounter #14. This procedure is in place so that veterans who do not perceive benefit from the treatment [i.e. those receiving sham stimulation] will continue to treat themselves per protocol; this is critical for the overall purpose of the study in order to be able to infer that it was the active treatment that produced the therapeutic effect. If subjects did not continue stimulating themselves, we would be unable to determine whether a placebo effect existed or not.

Encounter 7 – Phone Call: Within 7 ( $\pm 4$ ) days after Encounter 6 (Day 0), subject will receive a phone call from study personnel to inquire about any negative effects of stimulation (Adverse Events, AEs) and to check if they are using the diary after each stimulation.

Encounter 8 – Phone Call: Within 23 ( $\pm 4$ ) days after Encounter 6 (Day 0), subject will receive phone call from study personnel to inquire about AEs, check as to use of diary, rating of widespread pain over past 24 hours on a 10-point VAS, and potential desire to reduce medications.

Encounter 9 – Phone Call: Within 46 ( $\pm 4$ ) days after Encounter 6 (Day 0) subject will receive phone call from study personnel to inquire about AEs, check as to use of diary, rating of widespread pain over past 24 hours on a 10-point VAS, and potential desire to reduce medications.

Encounter 10 – Phone Call: Within 63 ( $\pm 4$ ) days after Encounter 6 (Day 0) subject will receive phone call from study personnel to inquire about AEs, check as to use of diary, rating of widespread pain over past 24 hours on a 10-point VAS, and potential desire to reduce medications.

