Encounter 11 – Phone Call: Within 65 ( $\pm 4$ ) days after Encounter 6 (Day 0) subject will receive phone call from study personnel to rate their widespread pain over past 24 hours on a 10-point VAS. .

Encounter 12 – Phone Call: Within 67 ( $\pm 4$ ) days after Encounter 6 (Day 0) subject will receive phone call from study personnel to rate their widespread pain over past 24 hours on a 10-point VAS.

Encounter 13 – Phone Call: Within 69 ( $\pm 4$ ) days after Encounter 6 (Day 0) subject will receive phone call from study personnel to rate their widespread pain over past 24 hours on a 10-point VAS.

Encounter 14 – Office Visit: Within 70 ( $\pm 4$ ) days after Encounter 6 (Day 0) subject will come to ISMMS. They will provide the 5th pain rating to arrive at the median pain rating. They will fill out same questionnaires they filled out on study Encounter 6 as well as the patient global measure of change and the measure of certainty, and will provide information about AEs and medication changes. They will again have the same brief medical evaluation as was done on Encounter #6 to provide data as to whether they fulfill criteria for GWI, CFS, IBS, MCS or FM. They will exit the blinded part of the study and return their original unit. Subjects who have completed at least 70% of diary entries will be given the active unit and will be trained on it again. They will be given new paper diaries and sent home. They will continue to use their electronic diary logon information to access their diary.

	Protocol Name:	Vagus Nerve Stimulation: A Non-Invasive Treatment to Improve the health of Gulf Veterans with Gulf War Illness
	Principal Investigator:	[name]
	Primary Contact Name/Contact Info:	[name]: [contact]
	Date Revised:	07/15/2019
	Study Number:	HSM# 16-00097

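### The headache-day question is asked only after the day's final device treatment, so headache records can depend on device use, and no source for the headache-day endpoint is named

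*Combined protocol and SAP*

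**What the plan says.** Section 5 e) lists as a secondary endpoint the difference between arms in "change in number of migraine/headache days in the final week of the randomized/blinded period from the week prior to randomization".

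Section 5 f), under the source data, ties diary entries to treatments: "Patients will be required to complete a diary after they self administer each treatment to each side of his/her neck". The headache item comes at the end of that sequence: "After the final treatment for that day, the diary asks the patient if s/he has had a headache lasting at least 4 hours". The online version has the same trigger: "The electronic diary mirrors the paper diary, except that it is online with a secured web address". The Encounter 6 text describes the diary as "to be completed after each of the three daily treatments".

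The same list of source data contains a separate past-week migraine-day count, with the definition "A migraine day is one where a patient has a headache lasting at least 4 hours". No encounter is said to administer it. Encounter 6 names MIDAS, SF-36 and HADS. Encounter 14 repeats those and adds the global-change and certainty measures.

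Participants are told that both device use and diary completion must reach 70%, but only the diary part is enforced: "Subjects who have completed at least 70% of diary entries will be given the active unit". The reason given for the instruction begins "This procedure is in place so that veterans who do not perceive benefit from the treatment"; the protocol identifies these veterans as the sham group and wants them to keep treating. In section 5 h), the only missing-data rule records dropouts as unchanged from baseline. Nothing is said about single blank diary days.

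**The concern.** An outcome should be recorded on the same schedule whether or not the patient took the treatment. Here the only described day-by-day headache question depends on a treatment session. A participant who leaves the device alone on a given day, perhaps because of a bad headache or because it does not seem to help, has no described occasion to report a headache.

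The protocol raises the possibility that device use will fall in the sham arm. If it does, the chance that a headache day is recorded would differ by arm for reasons unrelated to headache frequency. In a trial aiming for 40 evaluable subjects, with migraine present in only some of them, a modest difference in recording could distort this comparison.

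**Working it through.** The plan states no expected headache-day count, variance or sample size for this endpoint, so there is no figure of its own to reproduce. Its sample size of 26 concerns pain and has no bearing here.

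**1. Which days carry a prompt.** The phrase about the final treatment can be read in two ways.
- Reading A, the third scheduled session: any day without that session has no described prompt.
- Reading B, the last session actually taken: only a day with no session at all has none.

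**2. Whether the 70% diary rule protects the item.** Inputs are three sessions a day (Encounter 6) and a 70-day blinded phase (Encounter 14).
- Entries: 3 × 70 = 210. Threshold: 0.70 × 210 = 147. Entries that may be missed: 210 − 147 = 63.
- Reading A, all seven third sessions of the final week missed: (210 − 7)/210 = 203/210 = 97%. Passes.
- Reading B, no session at all in the final week: (210 − 21)/210 = 189/210 = 90%. Passes.

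Under either reading, a participant can meet the enforced rule with no headache answer in the endpoint week. Counting each side of the neck separately (6 × 70 = 420) leaves these percentages unchanged.

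**3. Timing.** No look-back window is stated. If the last session were at 20:00 (an assumed time), a headache starting after 16:00 could not yet have lasted 4 hours when the question is put. This gap exists even with full adherence. Nothing shows that it differs by arm.

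**4. The baseline week.** The endpoint is a change from the week before randomization. Diary training takes place at Encounter 6, the randomization visit, so this diary cannot supply that week. The four screening calls (Encounters 2 to 5) are described as collecting pain ratings only. The source of the baseline count is therefore not stated.

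**5. Illustration.** Two assumptions are not in the documents: a given number of true headache days a week, and blank days counted as no headache. Prompts are missed at random.

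Recorded days = true days × (prompts answered / 7)

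| True days | 1 prompt missed | 2 prompts missed |
|---|---|---|
| 2 | 2 × 6/7 = 1.71 | 2 × 5/7 = 1.43 |
| 3 | 3 × 6/7 = 2.57 | 3 × 5/7 = 2.14 |
| 4 | 4 × 6/7 = 3.43 | 4 × 5/7 = 2.86 |

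For a difference between arms, take 3 true days in both and no treatment effect. If 10% of active days and 30% of sham days lack a prompt, the recorded counts are 3 × 0.9 = 2.7 and 3 × 0.7 = 2.1, a spurious 0.6 day against active. Exchanging the percentages gives 0.6 day in favour of active. Equal percentages give zero.

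**6. Whether proration alone is enough.** Suppose treatment is skipped on 30% of headache days and 10% of other days (assumed). With 3 headache days and 4 others, answered headache days are 3 × 0.7 = 2.1 and answered other days are 4 × 0.9 = 3.6. The prorated count is 7 × 2.1/(2.1 + 3.6) = 2.58, not 3. Scoring over answered days therefore does not fully repair a prompt tied to treatment.

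**The case against.** The strongest reply is that the endpoint may not come from the diary at all. The past-week item has the same one-week window as the endpoint and would not depend on sessions, and some source other than the diary is needed for baseline in any case. That is fair, and it means the documents do not establish that the endpoint is measured through treatment entries. But no encounter collects the past-week item, and the diary is the only headache-day collection with a described procedure. The gap remains until the source is named.

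Three stronger readings are tempting and should not be adopted.
- *Blank days are scored as headache-free.* The documents give no rule for single blank days, so this is only one possible scoring.
- *A participant could qualify with headache answered on only 7 of 70 days* (two sessions daily give 140 entries, plus seven third sessions). This holds only under Reading A. Under Reading B each of those days yields an answer.
- *The sham count will be too low and the comparison biased in a known direction.* Lower use in sham is the protocol's worry, not an observed fact, and the illustration reverses if active users skip more.

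There are also safeguards. Staff ask about diary use by phone at Encounters 7 to 10, the last at about day 63, and participants believe device use counts towards open-label access. These should reduce missed sessions. They do not create a headache prompt on an untreated day. The electronic form pages are in the attached IDE application, so the actual layout could be better than the protocol text suggests.

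**Conclusion.** The point holds in a limited form. As written, both diary versions link the headache question to the day's final treatment, describe no prompt on an untreated day and give no look-back. The 70% rule does not secure any headache answer in the endpoint week. Because the protocol itself anticipates less treatment among sham users, missing headache records could differ by arm. The source of the count is unstated for both weeks, and the diary cannot supply the first.

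The size and direction of any bias are unknown. The recorded counts of 2.6 and 2.1 days against 3, and the 0.6-day spurious difference, rest on assumed headache frequency, assumed missed prompts and an assumed scoring of blanks. They show scale and are not predictions. The matter concerns one secondary endpoint. The primary pain ratings are taken by phone and at visits and are unaffected. It is a cheap improvement worth making, not a threat to the main result.

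**What to change.** 1. Detach the headache item from the treatment entries. Ask once every calendar day, whether or not the device was used, about a headache of 4 hours or more in the preceding 24 hours.
2. Name one source for both weeks. Either collect headache days in the same daily way in the week before randomization, or administer the past-week item at Encounters 6 and 14 and declare it the source for both.
3. If the daily item is used, add a scoring line to section 5 h): yes-days divided by days answered, times 7, with a stated minimum number of answered days. Unanswered days are not counted as headache-free.

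The cost is a small change to the paper and electronic forms and a few lines of analysis text, with one extra prompt on untreated days and no added visit. Daily collection before Encounter 6 would also need a form for the screening week; the past-week item avoids that but relies on recall. The payments section refers to subjects who have already taken part, so some data will have been entered under the old prompt. Those records should be flagged in the analysis.

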**The Three Phases of the Study**

**Subject Identification Phase of Study**

Encounter 1: face to face visit at the WRIISC at EOAMC for subject identification, consent, enrollment and screening. At this visit Participants will sign a consent document, complete several surveys including the PCL5 and PHQ8, a history and physical, vital signs and a 12 lead electrocardiogram (ECG) performed by a trained clinician. Veterans who complete screening criteria will begin the blinded phase of the study if they wish to do so. They will receive additional information about the risk, benefits and function and operations of the neuro-stimulator at ISMMS through a separate informed consent process occurring with ISMMS Investigators at ISMMS. No other study procedures with the Veterans will be done at the EOAMC.

Encounters 2-5: 4 phone contacts done in the week after Visit 1 to assess pain in the past 24 hours.

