**4) Resources Available to Conduct the Human Research**

The call for proposals leading to the current study required individual investigators to partner with industry. The preliminary data on which the current proposal builds had been collected via an NIH grant using a surgically implanted VNS device. The company making this implanted device had no interest in using it in pain syndromes, and the cost of the device as well as the costs for implanting it made it impractical for large scale use. In the meantime, it came to the attention of [name], the PI, that electroCore (eC) Ltd. was manufacturing and testing a rechargeable, externally delivered, transcutaneous device for VNS. As published preliminary clinical efficacy data using this device were encouraging and the use of the device less cumbersome and more economical, he approached eC to partner with him in this study to fulfill the requirements of the Department of Defense (DoD) contract for partnership with industry. That partnership led first to a LOI which was approved and then the full proposal which was funded at the end of the last government fiscal year. Thus the work will be done at ISMMS in collaboration with eC.

Recruitment goals and determination of sample size: Sample size was determined based on Lange et al.’s published paper on implanted VNS in non-veterans [i.e., 12 evaluable patients] on which [name] was the senior author. In these participants mean pain severity decreased by 4.2 units on a scale from 0 to 10 over a 3-month period of active stimulation, a large effect (Cohen’s d = 1.92). Based on this result, we tested the power to determine a large effect of VNS condition (Cohen’s  $f^2 = .35$ ) on post-intervention pain-severity, controlling for pre-intervention pain severity. The power analysis was conducted with G\*Power 3, specifying a standard Type I error ( $\alpha = .05$ ) and desired power of .80. Results indicate that a total sample of 26 would be sufficient. Given a sample of 40, the proposed research should be amply powered to detect a condition difference in pain severity, even allowing for attrition. Therefore, we will target enrollment to obtain data from 40 evaluable subjects. We are requesting IRB permission to screen as many as 100 patients to get to the desired sample size. Since our associates at the EOVAMC’s WRIISC are already involved in other GWI studies, we expect no problem in attaining this target.

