We will initiate recruitment by having the research study coordinator, who will be an MSBI employee working half time at MSBI and half time at the WRIISC, contact the 86 Gulf veterans who have reported having WSP and who have consented to be contacted for potential research studies. These 86 subjects should be a large enough recruitment group to achieve the required sample size of 40 participants (we are budgeting for 44 participants to allow for drop out). If additional subjects are needed for study, the research study coordinator will identify these from the remaining approximately 400 Gulf veterans whose contact information has been collected at the WRIISC and who have agreed to be contacted for research. The coordinator will call subjects, as needed, and collect symptom information to determine if they may have GWI with widespread pain. Subjects will then go to the WRIISC to learn about this study, go through the necessary screening and sign their informed consent to allow their PHI to be transmitted to ISMMS. Veterans will also be given a brochure summarizing what they will expect during the study and a schedule of all visits, both phone and face to face. We have developed flyers which will be distributed to places that Gulf veterans will see to inform them about the study, which includes health and veteran related online websites, in addition to being distributed over a course of time to veteran emails and to mobile devices.

General study info will also be posted on the Pain and Fatigue Study Center’s website [painandfatigue.com] for informational purposes, as well as for possible subject recruitment. The specific text that will be posted on the website is included with the study submission in a file titled “Website Info.”

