	Date Revised:	07/15/2019
	Study Number:	HSM# 16-00097

13. Patient expresses widespread pain of < 5 on the numeric scale of 0-10 Pain VAS on the first encounter at the WRIISC in EO VANJ.
14. Patient has a history of non-epileptic or epileptic seizures within the last 5 years.
15. Patient, in the opinion of the investigator, has a known history or suspicion of substance abuse or addiction within the last 5 years.
16. Patient, in the opinion of the investigator/research staff, is incapable of operating the gammaCore-R device as intended and performing the data collection procedures.
17. Patient has a self-reported psychiatric or cognitive disorder and/or behavioral problem which in the opinion of the clinician may interfere with the study (e.g. Bipolar Disorder, depressive disorder with psychotic features, Specific Phobia, Acute Stress Disorder).
18. Patient is pregnant or thinking of becoming pregnant in the next 6 months, or is of childbearing years and unwilling to use an accepted form of birth control or is unwilling to undergo pregnancy testing.
19. Patient is nursing.
20. Patient has undergone botulinum toxin (BOTOX) injections of the head and/or neck in the last 3 months.
21. Patient is participating or has participated in any other therapeutic clinical investigation during the last 30 days.
22. Patient belongs to a vulnerable population or has any condition such that his or her ability to provide informed consent, comply with follow-up requirements, or provide self-assessments is compromised (e.g., homeless, developmentally disabled, prisoner).
23. Patient has evidence of suicidality based on question #9 from the Patient Health Questionnaire [PHQ] - 9.
24. Patient has previously used a gammaCore device.
25. Patient is the spouse or housemate of someone else in the trial.

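### The suicidality exclusion relies on question #9 of the PHQ-9, but the only PHQ form named in the visit schedule is the PHQ8

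*Combined protocol and SAP*

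**What the plan says.** Two places in the combined protocol and SAP name a PHQ form.

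- **Section 5 b), Exclusion Criteria, item 23:** "Patient has evidence of suicidality based on question #9 from the Patient Health Questionnaire [PHQ] - 9". The criterion specifies both the instrument and the item.
- **Section 5 f), Subject Identification Phase, Encounter 1** (the VA screening visit): veterans "complete several surveys including the PCL5 and PHQ8, a history and physical, vital signs". The form named here is the PHQ8.

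The route from screening to randomisation crosses two institutions. Under Section 5 a), veterans attend the VA centre to "go through the necessary screening and sign their informed consent to allow their PHI to be transmitted to ISMMS". Encounters 2 to 5 are "4 phone contacts done in the week after Visit 1 to assess pain in the past 24 hours". Encounter 6, at ISMMS, is described as "Confirmation of eligibility, randomization and device and diary training Visit". At that visit, once the fifth pain rating has been taken, "Then medical and eligibility information obtained on Encounters #1 through 5 will be briefly reviewed".

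**The concern.** A criterion tied to one numbered question can be applied only if the form that contains the question is completed. The schedule names a form with a different number, and that name suggests eight questions rather than nine.

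The division of work between sites adds to the difficulty. VA staff who follow the Encounter 1 text literally would give the PHQ8. ISMMS staff who apply item 23 literally would look in the transferred record for a PHQ-9 question #9 response, and might not find one.

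Item 23 is the only eligibility criterion that names suicidality. What is at stake is participant safety and the ability to show that the criterion was checked before randomisation. The estimand, the sample size and the ANCOVA are unaffected.

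**Working it through.** The plan states no figure to reproduce, so the check is a reading of every mention of a PHQ form and of every questionnaire named by encounter.

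| Place | PHQ form named | What it provides |
|---|---|---|
| 5 b), exclusion 23 | PHQ-9, question #9 | Defines the exclusion |
| 5 f), source data list | None | Describes SF-36, MIDAS, HADS, the diaries and others |
| 5 f), Encounter 1 | PHQ8 | Screening surveys at the VA |
| 5 f), Encounters 2–5 | None | Pain ratings by telephone |
| 5 f), Encounter 6 | None | Review of Encounters 1–5, then MIDAS, SF-36 and HADS |
| 5 f), Encounter 14 | None | Encounter 6 questionnaires plus global change and certainty |
| 5 f), Encounter 22 | None | As Encounter 14, without certainty |

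**Mentions.** There are 2 mentions of a PHQ form, with 2 different form numbers. The PHQ-9 appears only in the exclusion list and the PHQ8 only at Encounter 1.

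**Where the response could come from.** The Encounter 6 questionnaires are completed only after the subject is judged still eligible, and HADS is not the instrument item 23 names. Encounters 2 to 5 are described as pain calls. The text also says the VA site performs no study procedures beyond the screening visit. As written, Encounter 1 is therefore where the response would be obtained, and the PHQ form named there is not the one the criterion uses.

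**Criteria.** Inclusion items 1–7 and exclusion items 1–25 give 7 + 25 = 32. One of the 32, item 23, names suicidality. Exclusion 17 covers self-reported psychiatric disorder on clinician opinion and does not mention suicidality.

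**Bounds on people affected.** Section 4 says "We are requesting IRB permission to screen as many as 100 patients to get to the desired sample size".

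- Lower bound: 0, if PHQ8 is a slip or the item is collected separately.
- Upper bound: 100, if everyone screened completed only the named form and that form lacks the item.
- For those who go on to use a device, the corresponding range is 0 to 44, taking the 44 participants budgeted in Section 5 a) (also the ceiling in Section 1).

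These are limits from the text, not estimates.

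**The case against.** The strongest reply is that the document shows two labels that differ, not an item that goes uncollected. Four points support it.

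- The Encounter 1 list is open-ended. It also omits the pain VAS that exclusion 13 requires at the same visit, so absence from the list is weak evidence that something is not done.
- Item 23 is explicit, and "Veterans who complete screening criteria will begin the blinded phase of the study if they wish to do so". Staff who apply the criteria as written must obtain the PHQ-9 response.
- The document never describes the PHQ8, so the absence of a ninth question is inferred from its name.
- Section 5 h) places the eCRF pages in an attached IDE application that is not part of the public document. Those pages could settle the matter.

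There are also partial safeguards: the history and physical at screening, exclusion 17, and withdrawal in the subject's best interest under Section 5 j). The planned sharing of PHI shows no failure of transfer in itself.

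All of this limits the consequence, and the response may well be collected in practice. It does not remove the mismatch. Where the schedule does name a PHQ form, it is not the form the criterion specifies, and none of the safeguards replaces a criterion tied to one named item. If PHQ8 is only a slip, it concerns the form behind a safety exclusion and still needs correcting.

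**Conclusion.** The inconsistency is real and minor. Item 23 and Encounter 1 name different PHQ forms, and no other part of the document resolves the difference. Confidence in the mismatch is high, because it rests only on the two texts.

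Whether any response is missing cannot be determined from the document. That consequence would require the PHQ8 to have been used as named, to lack the item, and the item not to have been obtained in any other way. Under those assumptions the number screened without a response could reach the ceiling of 100; without them it is 0.

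**What to change.** 1. Reconcile exclusion 23 and the Encounter 1 text, so that the form named at screening contains the item on which the criterion relies.
2. Confirm that form against the eCRF page.
3. Ensure that the individual response, not only a total score or a pass/fail mark, is in the record seen at the Encounter 6 review, before randomisation.
4. For subjects already enrolled, record on file how criterion 23 was assessed.

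If the eCRF already holds the item, the cost is a wording correction. If it does not, the cost is a protocol and CRF correction, at most one questionnaire item at a visit already held, and a file check for those enrolled. No change to the sample size or analysis is needed.
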